Controls: 1) **Healthy control cases** will have a) average pain \leq 3/10 with menses or with withdrawal uterine bleeding from cyclical OCs and b) no concurrent chronic pain diagnoses or \geq 5 migraines in the past year. Healthy controls with < 2 migraines per year will be recruiting preferentially.

Exclusion criteria for dysmenorrhea (and D+COS), PBS and healthy control cases includes: a) presence of active pelvic or abdominal malignancies (primary or metastatic), b) absence of regular menses (including current pregnancy, recent pregnancy, or active breast feeding) c) active genitourinary infection in the last four weeks, d) unable to read or comprehend the informed consent in English, e) unwilling to complete study procedures f) presence of hypertension or risk for developing hypertension, and g) unwilling to withdraw from OCs for at least one cycle prior to the Phase #1 study visit. Participants with a history of epilepsy will not complete the visual unpleasantness task.

Inclusion/Exclusion Criteria for “Special” Healthy Controls and Chronic Pain Participants (Arm 2)

Special Healthy Controls (n=10) will be enrolled under the same inclusion and exclusion criteria as healthy controls, however, special healthy controls will not be required to have regular periods or abstain from hormonal contraception, and will not be assessed for migraines with aura.

Chronic pain cases (n=50) will have a diagnosed, documented (reviewed by PI) chronic pain disorder greater than six months' duration, which has required at least 2 different prescription treatments and/or surgical management. They must report an average pain of at least 5/10 in the last month. We will accept participants with any type of chronic pain (except for individuals with bilateral knee and hand pain) but anticipate many of our chronic pain participants to suffer from fibromyalgia, lower back pain, and chronic pelvic pain (including irritable bowel syndrome).

Of note, special healthy controls or chronic pain cases will not be excluded for unwillingness to undergo internal PPT testing, visual sensory testing, hip or head PPT. These groups may waive these procedures but still remain eligible to choose to participate in rest of the study.

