collected electronically using REDCap at home. If requested, paper versions can be provided instead and mailed in. For participants continuing to Phase 2, the year 1 annual medical history questionnaire will usually take place during their assessment #3 visit. All participants that complete phase 1 (Screen + Assessment #1), including phase 2 dropouts, will be asked to complete the annual follow-up questionnaire.

Group (Sample Size)	H (20)	D (20)	D+COS (95)	PBS (40)	P (50)	MSA
Bladder Pain at FU (VAS)	0	0	2.5	3.0	-	0.85
Pelvic Hyperalgesia (VAS)	0	0	3	3	-	0.84
Pelvic Hyperalgesia (Time)	0	0	2	2.5	-	0.83
Pelvic Pain Thresholds	0	.5	.5	2.3	-	0.81
Bodily Pain Thresholds	0	1.5	2	2	2.3	0.91
Conditioned Pain Modulation	0	1-2	1-2	4 _a	2-4 _b	0.94
Menstrual Pain History	0	3.7	5	6	-	0.81
Temporal Summation	0	0	.7	.8	-	-
Estradiol	0	1-3 _c	1-3 _c	1-3	-	0.84
Depression/Anxiety	0	.3	.4	2	2-4	0.82

Table X: Sample sizes and hypothesized results in Z-scores or range of Z-scores (relative to healthy) for subjects that are healthy (H), have dysmenorrhea (D), have cross organ sensitization (D+COS), PBS, or chronic pain (P). MSA indicates Kaiser's measure of sampling adequacy. Numbers in italics indicated minimum detectable hypothesized score with current sample size. Z-scores based on preliminary data, or others indicated by subscript (a: ⁹, b: ^{11,13}). Effects temporal summation in these populations are unknown, but effect sizes as large as 1.1 have been reported for fibromyalgia. Dashes (-) indicate unknown effect size.

C1.h Data Analysis/Sample Size Requirements: The primary outcomes under this hypothesis will be [1] bladder pain at FU, [2] pelvic hyperalgesia (VAS, time to return to baseline pain), reflecting peripheral dysfunction/sensitization, and [3] centrally mediated hyperalgesia (CPM, bodily pain thresholds).

Factor [1], Bladder pain at FU: Our preliminary data on healthy subjects and women with dysmenorrhea, in combination with other studies investigating migraine and PBS, suggests effect sizes between 1.4-5.6 (Cohen's d). As a control comparison, we expect that women with chronic pain will have levels of bladder and pelvic sensitivity comparable to healthy subjects. We will perform t-tests for each of these three pain variables using pairwise contrasts and appropriate Bonferroni corrections for six group comparisons.

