Factor [2], pelvic hyperalgesia: To confirm pelvic hyperalgesia (*but not necessarily pelvic PPT*) is higher in those with bladder pain, we will show bladder pain and pelvic hyperalgesia (both VAS and TIME) are higher in D+COS than healthy pain-free controls (H), dysmenorrhea only (D), and chronic pain patients (P). Similarly bladder pain, pelvic hyperalgesia and pelvic floor pain sensitivity (PPT) are anticipated to be greater in PBS than H, and D.

Factor [3], centrally mediated hyperalgesia: Greater central dysfunction manifest by impaired CPM and reduced bodily pain thresholds in vulnerable subjects will be shown by comparing D+COS, PBS, and P to D and H. We estimate 15 subjects per group will provide adequate power (g-power, a priori t-test, $\alpha=0.05$, $\beta=0.2$). To verify we have adequate phenotyping of CPM, we have included the positive control group with chronic pain (P). We assumed the

[figure not shown]
difference in CPM between healthy subjects and chronic pain patients in this protocol would have an effect size of 0.78 based on a meta-analysis (Lewis et al. 2012). Using a 2.6 allocation ratio, a priori power analysis ($\alpha=0.05$, $\beta=0.2$), suggests we need 20 healthy participants and as many as 50 chronic pain patients to detect a difference in the mean CPM. Additionally, the utilization of 50 chronic pain patients will allow us to use regression to identify up to 5 predicted factors associated CPM with correlation coefficients exceeding 0.3 even after correcting for multiple comparisons ($\alpha=0.05$, $\beta=0.2$) as suggested by an a priori random model power analysis. This will be readily captured as our global study design encompasses a larger sample size (Table X) to handle anticipated secondary analysis and projected needs for completion of Phase #2.

Additional confirmatory analysis: Special healthy control subjects (n=10), we will verify special healthy control subjects do not differ from original enrolled healthy control subjects (n=20) to ascertain chronic subjects (P) participating in the trial are not treated differently under blinded conditions.

For the secondary analysis of Phase #1, we will evaluate the D+COS (provoked bladder pain) phenotype while accounting for menstrual history (including historical OC exposure), hormonal factors, anxiety, and depression. To determine the relative contribution of these secondary variables on bladder pain, we will perform principal component analysis (PCA).

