C1.i Expected outcomes: (1) *Abnormal CPM is the primary predictor of widespread pain sensitivity observed in dysmenorrhea, D+COS and PBS.* Results would be insightful if CPM was worse in participants with D+COS and PBS than those with dysmenorrhea alone because this would indicate CPM mechanisms are involved in COS. On the other hand, if CPM impairments are universal across chronic pain patients, PBS, D, and D+COS compared to healthy controls, this would indicate that pain independent of location and chronicity depends on impaired descending inhibition. This finding would be the basis for developing a physiological biomarker for those at risk of developing CPP/PBS similar to approaches by others identifying risk for chronic pain^{45,79}. On the other hand, some pain conditions such as rheumatoid arthritis¹¹⁴ and trapezius myalgia¹¹⁵ do not seem to exhibit CPM. The vulnerability to conditions unrelated to CPM may involve either inflammatory or specific peripheral nerve events. If CPM does not correlate with widespread pain sensitivity or bladder pain phenotypes in this proposal, we have adequately powered our sample size to detect alternative mechanisms that could be responsible (e.g. menstrual, hormonal, psychological). Nevertheless, consistent with meta-analyses on the menstrual cycle⁵⁴, psychological⁵⁵, and central factors on pain⁵⁶, we anticipate central pain factors to explain the majority of the variance in bladder pain sensitivity. Determining the relative importance of systemic E2 concentrations vs. other modifiable factors such as

menstrual pain will provide insight on the most important mechanisms for reducing bladder pain sensitivity in vulnerable women.

(2) *Pelvic hyperalgesia and severity of menstrual pain are more common in D+COS phenotype vs. dysmenorrhea only.* The identification of clinical biomarkers such as severity of pain after a speculum exam (analogous to the post pelvic floor PPT pain report) can be obtained from our results. Our study results would provide evidence of the significance of this routine clinical exam in reliably predicting bladder sensitivity.

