C1.j Potential Problems: *Primary and/or secondary comparisons are nonsignificant: a mixture of mechanisms are involved in D+COS phenotype or PBS.* We will confirm whether our paradigm was sufficient to detect deficits in CPM using our positive control group with chronic pain to validate a true negative finding. Afterwards, we will use cluster analyses to identify phenotype patterns and confirm mechanistic differences with banked serum. *Why not examine additional hormones?* We are examining hormones that have been frequently studied in pain research and will bank serum allowing for the future possibility of studying others. *What about endometriosis, fibroids and other known anatomic uterine pain conditions?* To account for the common conditions (especially within our medical practice), we will include 10 confirmed endometriosis (operative report review) participants and 10 fibroids participants (ultrasound or surgical confirmation) mixed within our dysmenorrhea cohort to determine which effects produced by the primary analysis are due to anatomical conditions.

C2. Methods for Phase #2

C2.a Participation criteria

All phase #1 participants with D+COS (pool of 95 candidates) or PBS (pool of 40) will be enrolled with intent to transition into phase #2, though the second phase of the study will be presented as optional. If they choose not to participate in their randomized group, they will have the option to come back in a year later for an additional assessment visit for long term follow up data. These enrollment targets, accounting for a potential 35% dropout rate, will enroll 62 participants with D+COS and 26 PBS. This will provide adequate power for the prespecified contrasts.

Inclusion Criteria: 1) Participation in Phase #1 and assigned to the Arm #1 PBS or D+COS group, 2) willing to comply with OC assignment (continuous for PBS; cyclical, continuous, or no OC for D+COS).

Exclusion Criteria: a) presence of active pelvic or abdominal malignancies (primary or metastatic), b) absence of regular menses (including current pregnancy, recent pregnancy, or active breast feeding), c) unwilling to undergo pelvic examination/testing, e) standard contraindications to use of OCs:

- Thrombophlebitis or thromboembolic disorders, or a history thereof
- Cerebrovascular or coronary heart disease
- Known or suspected carcinoma of the breast
- Endometrial cancer or other known or suspected estrogen-dependent neoplasia
- Undiagnosed abnormal genital bleeding

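### A CPM deficit in the chronic pain group shows that the test works; it cannot turn a non-significant CPM result in D+COS or D into a true negative, and the plan has no interval criterion that could

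*Combined protocol and SAP*

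**What the plan says.** Section C1.j (Potential Problems) plans for the case "Primary and/or secondary comparisons are nonsignificant". It first attributes such a result to a mixture of mechanisms. It then says the study will confirm that the paradigm could detect CPM deficits, "using our positive control group with chronic pain to validate a true negative finding", and that cluster analyses and work on banked serum will follow.

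Section C1.h sets the CPM contrasts under Factor [3]: central dysfunction "will be shown by comparing D+COS, PBS, and P to D and H". The one CPM sample-size calculation there with a stated effect is for H v P: effect size 0.78, allocation ratio 2.6, alpha 0.05, power 0.80, giving 20 healthy and up to 50 chronic pain participants. The only other CPM sizing is 15 per group, with no effect size. Under Factor [1] the section also promises "appropriate Bonferroni corrections for six group comparisons".

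Table X lists H = 20, D = 20, D+COS = 95, PBS = 40 and P = 50, and hypothesises a CPM Z-score of 1-2 relative to healthy for both D and D+COS. Section B.1 gives different Phase 1 completer numbers: 40 healthy, 43 chronic pain and 515 with dysmenorrhea, the last not split into D and D+COS.

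**The concern.** A positive control answers one question: could this test, in these hands, show a deficit where one is expected? Whether the deficit in D+COS or D is small enough to call absent is a different question. The answer depends on the precision of the D+COS and D contrasts, which have their own group sizes. The documents state no smallest relevant CPM deficit, no equivalence margin and no interval criterion for these contrasts. Followed as written, C1.j lets a non-significant result plus a working positive control be labelled a true negative when the data may still be compatible with a sizeable deficit.

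The D+COS v D contrast carries weight. Section C1.i says that worse CPM in D+COS and PBS than in dysmenorrhea alone would point to CPM mechanisms in COS. An imprecise null there, reported as a negative, would be an unsupported conclusion on a central hypothesis.

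**Working it through.** **Inputs.** Group sizes come from Table X, with the alternatives in section B.1. The 0.78 SD for P v H, alpha 0.05 and power 0.80 come from C1.h. Two levels are shown, 0.05 and 0.05/6 = 0.0083, because it is unclear whether the six-comparison Bonferroni, placed under Factor [1], also covers CPM. Tests are taken as two-sided. The 0.5 SD deficit is an assumption made here. Table X gives 1-2 v healthy for both D and D+COS, so it leaves their difference unspecified (anything from 0 to 1 SD fits).

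**The plan's own figure.** A two-sided noncentral t calculation with d = 0.78 and ratio 2.6 gives 19 + 49 (power 0.81), which agrees with the stated 20 and 50. A one-sided test would need only 15 + 39, so the plan's figure is two-sided and unadjusted. Power at 20 v 50 is 0.828 at 0.05 and 0.593 at 0.05/6.

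**Miss rate.** With SD = 1, SE = √(1/n₁ + 1/n₂) and noncentrality = d/SE. The miss rate is the probability that |t| stays below its critical value.

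D+COS v D, 95 v 20, d = 0.5: SE = √(1/95 + 1/20) = 0.246; noncentrality = 0.5/0.246 = 2.03; critical t (113 df) = 1.98 at 0.05 and 2.685 at 0.05/6. The miss rate is 0.478 and 0.738.

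| Contrast | Sizes | True deficit | Missed at 0.05 | Missed at 0.05/6 |
|---|---|---|---|---|
| D+COS v D | 95 v 20 | 0.5 SD | 48% | 74% |
| D+COS v D | 95 v 100 (illustrative) | 0.5 SD | 6.5% | 21% |
| D+COS v H | 95 v 20 | 0.5 SD | 48% | 74% |
| D+COS v H | 95 v 40 | 0.5 SD | 25% | 51% |
| D+COS v H | 95 v 20 | 1 SD | 2% | 9% |
| D v H | 20 v 20 | 0.5 SD | 66% | 87% |

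D v H is not among the Factor [3] contrasts, but C1.i relies on it when it considers the case "if CPM impairments are universal across chronic pain patients, PBS, D, and D+COS compared to healthy controls".

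**Missed deficit together with a successful positive control.** D+COS v D and P v H share no group, so the probabilities multiply. With Table X sizes for both contrasts:

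- at 0.05: 0.478 × 0.828 = 0.40
- at 0.05/6: 0.738 × 0.593 = 0.44

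If P has the larger deficit that Table X hypothesises (Z of 2-4), the control almost always succeeds and these figures rise to the full miss rates of 48% and 74%.

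**Precision.** The confidence-interval half-width for 95 v 20 is 1.98 × 0.246 = 0.49 SD at 95% and 2.685 × 0.246 = 0.66 SD at the corrected level. An estimate of zero at the corrected level would therefore still be compatible with a deficit above 0.5 SD.

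**The case against.** **C1.j is mainly an assay-sensitivity check.** It asks whether the paradigm could detect deficits, and further analyses follow. That is fair: the check is sound and should stay. What fails is the inference attached to it, that it validates a true negative. The later cluster analyses do not remove that label.

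**The plan expects larger effects.** At 1 SD, D+COS v H is missed only 2% of the time (9% corrected) even with 20 healthy women. This stands for comparisons with healthy women. It does not carry over to D+COS v D, where Table X implies no particular difference.

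**D may be much larger than 20.** This also stands. If D+COS is 95 of the 515 women in section B.1, D could be as many as 420, and at D = 100 the problem is already modest. The section B.1 sizes for H and P (40 and 43) should therefore not be combined with the Table X D group of 20; doing so inflates the joint probability.

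**Stronger readings that the documents do not support.** A reader might infer that a null P v H result would be taken as proof that the paradigm failed, which would be doubtful because C1.i says that "some pain conditions such as rheumatoid arthritis" do not seem to exhibit CPM while the Arm 2 criteria say "We will accept participants with any type of chronic pain". The plan never states that converse. A reader might also infer that this check triggers the turn to menstrual, hormonal or psychological explanations. C1.i does not tie those to it, and C1.h examines such factors by principal component analysis in any case.

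**Conclusion.** The point holds as a gap in the inference. A significant P v H difference cannot establish that CPM is unimpaired in D+COS or D, and nothing else in the plan does. That conclusion needs no assumed effect size.

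The size of the risk is conditional. For a 0.5 SD deficit of D+COS v D at Table X sizes, a miss alongside a successful control occurs about 40% of the time at 0.05 and 44% at 0.05/6. This rests on the assumed 0.5 SD, D = 20, P v H at 0.78 SD and two-sided tests. A single general percentage for how often a real deficit would be wrongly called negative is not supportable, because the rate changes several-fold with the contrast, the size of D and H, and the multiplicity rule.

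**What to change.** - In C1.j, describe P v H as an assay-sensitivity check only, and remove the statement that it validates a true negative.
- Report confidence intervals for the CPM contrasts D+COS v D and D+COS v H, at the level that the multiplicity rule requires, and state whether the six-comparison correction covers CPM.
- Fix a smallest relevant CPM deficit before analysis. Call a result negative only if the interval excludes it; otherwise report it as inconclusive.
- Reconcile the group sizes in Table X with those in section B.1, including the split of the 515 into D and D+COS.

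**Cost.** The change is to wording only, with no new participants or procedures, but it affects what can be concluded. For 95 v 20 and a 0.5 SD margin, the estimate must fall below 0.5 − 0.487 = 0.013 SD at 95%, or below 0.5 − 0.661 = −0.161 SD at the corrected level. With a true difference of zero and SE 0.246, that happens about 52% and 26% of the time. So about half to three quarters of genuinely null results on that contrast would be inconclusive, and fewer if D is larger.

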C2.c Trial of OC usage: Participants in Phase #2 of the study will be prescribed generic microgestin (20 µg ethinyl estradiol/1 mg norethindrone acetate), a lower estrogen-containing OC well-tolerated by women. Microgestin has minimal breakthrough bleeding compared to a continuous OC regimen with higher estrogen concentration or different progestin⁵⁷ or a cyclic paradigm with lower estrogen concentration.⁵⁸ D+COS participants will be randomized into three study arms: cyclical OC usage (n=26) vs. continuous usage (n=26) vs. no OC (n=10). Less untreated subjects are needed as large effect sizes are expected compared to OC users. Cyclical OC users will be instructed to take 21 days active followed by 7 days of no pills every four weeks. Continuous OC users will be instructed to immediately start the next pack of active pills on day 22. Those not taking OCs will be instructed to use barrier contraception. At the time of randomization, participants will be counseled by the study team on the proper usage of these treatments. Participants assigned to OCs will receive a three or four month prescription for microgestin and have it filled at the Evanston Hospital Outpatient Pharmacy. All refills will be distributed by the same pharmacy. Separately from the D+COS randomization scheme, PBS participants will receive only continuous OC. This study design deliberately avoids randomizing chronically symptomatic PBS patients onto cyclical vs. continuous OCs, as the anticipated difference in outcomes is small, and therefore not likely to be favorable in recruiting subjects. However, identifying which pain mechanisms (visceral and pelvic sensitivity) change following OC-induced hormonal suppression both in chronically symptomatic PBS sufferers vs. the

asymptomatic D+COS patients may prove crucial to understand which PBS patients exhibit hormonally responsive pain.²³

C2.d Study Visits Participants in Phase #2 will return to repeat experimental pain and sensory assessments identical to the initial Phase #1 and complete the questionnaires referred to in the screening visit plus a side effects questionnaire at six months and one year after OC initiation (which follows a two month washout in Phase #1). These visits should occur on pill days (not cycle days) 7-21 of the cyclical group and any day for the continuous group, which is comparable to cycle days 15-28 in Phase #1. Control subjects not taking OCs will participate during their post-luteal phase days 15-28 (similar to Phase #1). This will make hormonal levels comparable and minimize any vaginal bleeding. For those who are randomized to Phase 2 but decides to not participate in their randomized group, they may be asked to come in a year later for an additional assessment visit to obtain long term follow up data. These participants will be asked to complete daily diaries and ovulation kits for one month prior to the annual assessment visit, similar to Phase 1.

C2.e Home Assessments: Participants in Arm #2 will complete the daily diary during the fifth and eleventh month of OC administration^{33,60}. They will also complete a monthly questionnaire asking questions related to their pain, mental health, and any side effects they may be experiencing (comprised of the McGill Pain Inventory, a side-effects questionnaires, and PROMIS anxiety item bank, PROMIS depression item bank, and PROMIS pain interference item bank). They will not need to do these questionnaires during months 6 and 12 at home because they will do them during their study visit for assessments #2 and #3 respectively. When done at home, they should complete these assessments on or near day 15 of their pill pack for participants on cyclical OCP, day 15 of their menstrual cycle (15 days after their menstrual period started) for participants not taking OCPs, and simply 28 days apart for participants taking continuous OCP.

C2.f Compliance: To evaluate compliance, participants will be asked to return all used and partially used OCP pill packs.

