subject ID # (see data collection section D). Dysmenorrhea, healthy control, and PBS participants will be asked to fill out daily diary entries for all days between their screening visit and assessment #1. Participants in the special healthy control and chronic pain groups will be asked to complete daily diaries starting the day after their screen visit and continuing for 35 days, regardless of when their assessment visit is scheduled.

C1.d Washout for arm #1 participants on OCs (not relevant for arm #2): Those on OCs at enrollment will complete a washout lasting a minimum of one menstrual flow in order to accurately confirm dysmenorrhea severity with daily diaries. Bleeding that occurs within 7 days of the cessation of birth control pills will not be counted as a menstrual flow, since this is the result of withdrawal bleeding rather than menstruation. Thus, most women currently taking birth control pills will need to abstain from taking hormonal contraception for at least 7 weeks to allow time for a withdrawal bleed followed by one full menstrual cycle (4 weeks) plus the time it takes them to enter their luteal phase (approximately 3 weeks). In the case that a woman does not experience withdrawal bleeding within 7 days of the cessation of birth control pills, determination of whether the bleeding that does eventually occur is the result of delayed withdrawal bleeding or menstruation will be made on a case-by-case basis. In the case that we cannot confirm group eligibility from one menstrual flow on the daily diary (i.e. they did not have great enough pain), we may ask the participant to continue to abstain from hormonal contraception for a second menstrual flow. If they are still not eligible after two menstrual cycles, they will be deemed ineligible or if applicable (pain is 3 or less on all days), switched to the healthy control group.

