For the subset of participants who were using hormonal contraception to manage chronic or menstrual pelvic pain, and whom express concern about pain management during phase 1, the study doctor will discuss pain control options and if necessary, and the participant desires, prescribe Tylenol #3, Tramadol 50mg, or Norco 5/325. We expect these conditions to apply to a small subset of participants (less than 10). The participant may alternatively see their regular physician to address this issue. All other participants will be asked to manage their pain in the same ways they normally manage pain (e.g., over-the-counter painkillers, heat pads, etc.). All participants will be asked to indicate in their daily diary if they took any painkillers each day and if so, what medication and how much.

C1.e Assessment visit: Arm #1 and Arm #2 participants with regular periods and/or who are not using hormonal contraception will be asked to contact us when they start their first period after the assessment visit. The assessment visit will be scheduled during the anticipated participant's luteal phase (17-25 days after the start of their period adjusted if they typically have unusually short or long cycles). They also will be given ovulation kits and asked to complete them starting day 10 of their cycle up until their scheduled assessment visit to give us additional data about their menstrual phase. Bladder pain is less likely to be confounded with menstrual or ovulation pain during the luteal phase.

Special healthy controls and chronic pain participants (Arm 2) who do not have regular menstrual periods and/or are on hormonal contraception will not be required to use ovulation kits and instead visits will be scheduled at a time we do not expect any bleeding and approximately 2-6 weeks (but up to four months) after their screen visit.

The time between the screen visit and assessment visit may vary based on participant's personal schedule and ability to confirm ovulation status and group eligibility (if applicable) but will not exceed four months or be less than two weeks.

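### Sections C1.e and C2.d give different cycle-day windows for the same test, so untreated women's follow-up could be timed differently from their baseline and bias the Z1 comparison

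*Combined protocol and SAP*

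**What the plan says.** Section C1.e places Assessment #1, which is the Phase #2 baseline, in the "luteal phase (17-25 days after the start of their period adjusted if they typically have unusually short or long cycles". It gives the reason: "Bladder pain is less likely to be confounded with menstrual or ovulation pain during the luteal phase". Home ovulation tests are supplied too, and women are "asked to complete them starting day 10 of their cycle up until their scheduled assessment visit to give us additional data about their menstrual phase", so the kits supplement the calendar rule and do not replace it.

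Section C2.d sets the 6- and 12-month visits. Cyclical OC users come on pill days 7-21 and continuous users on any day, "which is comparable to cycle days 15-28 in Phase #1". For the untreated arm it says: "Control subjects not taking OCs will participate during their post-luteal phase days 15-28 (similar to Phase #1". It states no adjustment for cycle length. Its declared aims are comparable hormone levels and little vaginal bleeding.

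Three other places bear on the point:
- Section C2.i has ovulation kits mailed ahead of the 6- and 12-month visits.
- Section C2.h (Z1) compares OC users with untreated women on bladder pain by repeated measures ANOVA at 6 months against baseline, confirmed at 12 months, with E2 and P4 as covariates.
- Section C2.c allocates 26 women to cyclical OC, 26 to continuous OC and 10 to no OC.

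**The concern.** C2.d says twice that its window matches Phase #1, but C1.e gives a narrower, adjusted one. C2.d also labels its days post-luteal, where C1.e calls its window luteal. A coordinator who follows each section for its own visit would hold untreated women to one window at baseline and a wider one at follow-up.

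OC users' follow-up is set by pill day or is unrestricted, so the extra cycle days arise only in the untreated arm. Z1 rests on the contrast in change from baseline. If some untreated women are retested closer to ovulation or to menses than at baseline, their bladder pain could be higher because of timing alone. They would then seem to improve less, and the OC effect would look larger. With about 10 untreated women, a few visits can move the arm mean.

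**Working it through.** The plan gives no figure on this point to reproduce. The check compares the two windows and then illustrates the possible consequence.

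**Inputs**
- Baseline window: 17-25 days after period start, adjusted for unusual cycles (C1.e).
- Untreated follow-up window: days 15-28 (C2.d).
- Group sizes: 10 untreated, 26 + 26 = 52 on OCs (C2.c).
- Alpha 0.05 (C2.h, Table Z). Sidedness is not stated; two-sided is assumed.

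**Same scale?** Section C2.e counts "day 15 of their menstrual cycle (15 days after their menstrual period started", so day N means N days after period start and the windows can be compared directly.

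**Days outside the nominal baseline window**
- Baseline: 25 − 17 + 1 = 9 days. Follow-up: 28 − 15 + 1 = 14 days.
- Outside: days 15, 16, 26, 27 and 28, so 5/14 = 35.7%.
- If baseline counting is offset by one day (days 18-26), the days outside are 15, 16, 17, 27 and 28, again 5/14.

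**Women affected, if visits spread evenly over days 15-28** (an assumption; the documents give no distribution)
- Per follow-up visit: 10 × 5/14 = 3.6 women.
- At least one of two visits outside: 1 − (9/14)² = 59%.

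These figures count days. They do not measure bias.

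**Illustration of bias.** Suppose bladder pain is higher by δ (in SDs of the analysed score) on the five extra days, with no true OC effect and no shift elsewhere. Then bias = (5/14) × δ. The standard error of the contrast is √(1/10 + 1/52) = 0.345 SD. Type I error comes from 40,000 simulated two-sided t-tests per row, 10 against 52, as a simple stand-in for the repeated measures ANOVA.

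| Assumed δ (SD) | Bias favouring OCs (SD) | Type I error (nominal 5%) |
|---|---|---|
| 0.2 | 0.07 | about 5% |
| 0.5 | 0.18 | about 8% |
| 0.8 | 0.29 | about 14% |
| 1.0 | 0.36 | about 19% |

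If only days 15-16 carry extra pain, the fraction is 2/14 = 14%, or 1.4 of 10 women. The bias at δ = 1.0 is then 0.14 SD.

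**With one common window**, whichever it is, no follow-up day lies outside the baseline window. The expected bias from this source is 0, and the sample size does not change.

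**The case against.** The strongest reply is that this is a drafting slip. C2.d plainly believes that days 15-28 was the Phase #1 window, so one window was intended, and if staff used one there is no bias. That stands, and it is why the point is first a contradiction to be reconciled.

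Other parts of the reply also stand:
- The baseline window is flexible. C1.e adjusts it for unusual cycles, so some baseline visits may also fall outside days 17-25.
- In a 28-day cycle, days 26-28 are still luteal, and a woman who starts to bleed is at day 1 of a new cycle, outside days 15-28. C2.d's aim of limiting bleeding points the same way.
- Section C1.d allows "plus the time it takes them to enter their luteal phase (approximately 3 weeks". By that figure the early part of the baseline window can also precede the luteal phase, so the baseline did not cleanly avoid ovulation.

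The safeguards help but do not settle the matter. Nothing ties the visit day to a kit result, and a kit says little about nearness to menses. The E2/P4 adjustment is there to ask whether OCs act through circulating hormones. It may absorb some phase difference, but it is not stated to control visit timing.

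A reader might infer that the plan does inflate the OC effect, or that the 36% measures that inflation. The documents support neither: they report no rise in pain on the extra days and no distribution of visit days. A reader might also extend the bias to Z2. The reason in C1.e concerns bladder pain, whereas Z2 covers pelvic hyperalgesia, pressure-pain thresholds, temporal summation and CPM. An effect there is possible but not shown.

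**Conclusion.** The contradiction between C1.e and C2.d is certain from the text. Followed as written, it gives untreated women a nominal follow-up window 5 days wider than at baseline (14 against 9).

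The consequence is conditional. A bias in Z1, probably favouring OCs, requires that staff used different windows, that untreated visits fell on the extra days, and that bladder pain is higher on those days. Its size is unknown. In the illustration, a 0.2 SD shift leaves type I error at about 5%, while shifts of 0.5 to 1.0 SD take it to about 8-19%; both the shifts and the even spread of visits are assumptions. Z3 (PBS, before and after) and Z4 (continuous against cyclical) contain no untreated women and are unaffected. The point merits correction because the remedy is cheap and the untreated arm is small.

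**What to change.** Reconcile C1.e and C2.d so that untreated women are tested in one and the same cycle window, with the same cycle-length adjustment, at Assessments #1, #2 and #3. Use the ovulation kits already provided to confirm phase, and say how a result affects the visit date. Correct the post-luteal label and the statements that days 15-28 match Phase #1.

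For visits already done, report each untreated woman's actual cycle day at baseline and at each follow-up. Examine timing in Z1 only as a sensitivity analysis, for example by how closely baseline and follow-up cycle days agree among untreated women. Keep the full randomised set as the main analysis. Dropping only the untreated out-of-window visits would select after randomisation in one arm. Under the even-spread assumption it would leave about 10 × 9/14 = 6.4 women per visit, and about 10 × (9/14)² = 4.1 with both follow-up visits.

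The cost is a wording change and slightly less scheduling flexibility for about 10 women. No added participants or procedures are needed.
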